15.3. During first 3 weeks of afatinib treatment

- 15.3.1. Regular contact with patient to monitor adverse events, especially diarrhoea (phone contact allowed) according to treatment tolerability and investigator's decision.

15.4. Every visit during afatinib treatment

Visits will take place at 3, 6, 9 and 12 weeks after first dose, then every 4 weeks until stop of treatment.

- 15.4.1. Physical examination according to local standards, including blood pressure, performance status, and body weight
- 15.4.2. Check patient diary and count remaining tablets

- 15.4.3. Recording of symptoms / adverse events
- 15.4.4. Haematology: WBC, haemoglobin, platelets, neutrophils
- 15.4.5. If clinically indicated according to local standards: Chemistry; sodium (Na), potassium (K), calcium, albumin, magnesium
- 15.4.6. Serum creatinine and creatinine clearance calculated according to Cockcroft-Gault
- 15.4.7. Hepatic function: ALT, AST, bilirubin, GGT
- 15.4.8. Record all concomitant medication
- 15.4.9. Give to the patient the afatinib tablets for the next treatment cycle (3 or 4 weeks)

15.5. Imaging

The following imaging will be done on weeks 6 and 12 from day of first dose of trial treatment, and then every 8 weeks (weeks 20, 28, 36 etc) until progression:

- 15.5.1. CT thorax and upper abdomen

15.6. End of treatment visit

At the end of all trial treatment and **irrespective of the reason for stopping treatment**, an end of treatment visit at the centre is to be scheduled within 30 days following the last dose of trial treatment or within 30 days after planned treatment start if treatment never started. This visit has to be done for all patients, including those who did not start afatinib treatment. The following procedures should be performed:

- 15.6.1. Physical examination according to local standards, performance status, and body weight
- 15.6.2. Recording of symptoms / adverse events
- 15.6.3. Haematology: WBC, haemoglobin, platelets, neutrophils
- 15.6.4. Chemistry: sodium (Na), potassium (K), calcium, albumin, magnesium
- 15.6.5. Serum creatinine and creatinine clearance calculated according to Cockcroft-Gault
- 15.6.6. Hepatic function: ALT, AST, bilirubin, GGT
- 15.6.7. Pregnancy test for women of childbearing potential
- 15.6.8. CT thorax and upper abdomen, if not done within the last 6 weeks
- 15.6.9. Record all concomitant medication

15.7. Follow up after treatment stop, before progression

Follow up visits after trial treatment stop but before progression will take place every 8 weeks until progression; and should be scheduled at the same time as the CT scans

- 15.7.1. Report any pregnancy occurring within 6 months after treatment stop
- 15.7.2. Report any adverse event occurring within 90 days after treatment stop
- 15.7.3. Report any concomitant medication within 90 days after treatment stop

15.8. Follow up after progression

Follow up visits after progression will take place every 3 months until death or until 6 months from enrolment of the last patient, whatever occurs first.

- 15.8.1. Record survival status
- 15.8.2. Report any pregnancy occurring within 6 months after treatment stop
- 15.8.3. Report any adverse event occurring within 90 days after treatment stop
- 15.8.4. Report any concomitant medication within 90 days after treatment stop

16. Case report forms and documentation

16.1. Case report forms schedule

CRFs will only be available on-line at the Remote Data Entry (RDE) facility ETOPdata. No paper forms will be used, with the exception of paper SAE initial and follow-up forms in case of system unavailability.

Table 12. Case report forms

Tab in ETOPdata	To be completed
Eligibility for Enrolment	Within 28 days of start of baseline assessments
Baseline	Until 7 days after start of afatinib
Concomitant Medication	Continuously from signed informed consent to 90 days after end of trial treatment Within 7 days after each afatinib visit.
Trial Treatment Start Visit	Within 7 days after trial treatment start visit.
Afatinib Treatments	Within 7 days of the end of each cycle
Tumour Assessment	Baseline: Within 7 days after start of afatinib; Within 14 days after every imaging (weeks 6, 12 after start of afatinib treatment, and then every 8 weeks until progression)

Tab in ETOPdata	To be completed
Adverse Events	
Continously from signed informed consent to 90 days after end of afatinib treatment:
 
Within 7 days after enrolment (to record symptoms present at enrolment);
 
Within 7 days after each afatinib treatment visit;
 
End of treatment: Within 14 days after end-of-treatment visit if patient has been treated with afatinib.
 
In follow-up for 90 days after treatment stop

Pregnancy	
Within 24h of first documentation of pregnancy;
 
Within 14 days of end of pregnancy.

Serious Adverse Event Initial Report	
Within 24h of awareness of SAE or AESI;
 
Can be submitted via ETOPdata or via fax to ETOP Safety Office in case of unavailability of ETOPdata.

Serious Adverse Event Follow-up Report	
Within 14 days of completion of initial report.
 
If event was not resolved after 14 days, submit an additional report again within 7 days of resolution/final outcome of event.

End of Treatment	
Within 14 days after end of treatment visit (which is to take place within 30 days after end of treatment)

Follow-up	
To be completed within 14 days after each follow-up visit and at death.

Consult the ***CRF completion guideline*** for detailed instructions on how to complete, save and submit the electronic CRFs.

17. Statistical considerations

17.1. Primary objective

To evaluate the ability of afatinib to control disease in pretreated patients with advanced NSCLC harbouring *HER2* exon 20 mutations. Disease control is defined as complete or partial response, or disease stabilisation lasting at least 12 weeks.

17.2. Sample size determination

For sample size determination, a Simon's two stage phase II design [21] is adopted. A Disease Control Rate (DCR) of 50% is considered as unacceptable, targeting a DCR of 75%. Hence the null hypothesis under consideration is that the $DCR \leq 50\%$ versus the alternative that $DCR \geq 75\%$. For a one-sided type I error of 10% and power of 80%, a total of

22 patients need to enter the trial, with 9 patients in the first stage. If in the first stage, 6 out of the 9 patients achieve Disease Control, then the trial will proceed to the second stage and recruit an additional 13 patients for a total of 22 patients. If at the end of trial, at least 14 patients achieve Disease Control, then this finding will indicate that it would be reasonable to proceed to a Phase III trial.

17.3. Evaluation of primary and secondary objectives

The total trial duration will be approximately 40 months including a 6 months start-up period, 24 months accrual, 6 months follow-up after inclusion of the last patient, and 4 months for preparation of the final trial report.

The final evaluation of the trial will be performed approximately 40 months after the inclusion of the first patient.

The binomial exact one-sample test will be used for evaluation of the primary endpoint (DCR) at both the interim and final analysis (if trial continues to completion) [22-25]. The conclusion will be based on examining whether or not the observed number of patients who have achieved complete response, partial response and stable disease crosses the corresponding O'Brien-Fleming boundary. Results will be presented in terms of rates together with the corresponding exact binomial 90% confidence intervals.

The secondary endpoints of Progression free survival (PFS) and overall survival (OS) will be estimated by the Kaplan Meier method. Clinical efficacy will also be described by objective response rate (ORR).

Safety and tolerability of the afatinib treatment will be presented by tabulation of the CTCAE V4 grade. The safety cohort will encompass all patients who have received at least one dose of trial treatment.

Statistical analysis of both the primary and secondary endpoints will be described in detail in the Statistical Analysis Plan (SAP) document

17.4. Early stopping rules

An early look will take place at the end of the first stage, when 9 patients are evaluable for the primary endpoint. This report will be submitted to the Independent Data Monitoring Committee (IDMC), see section 20.3. If less than 6 patients achieve Disease Control, then the results will be reported immediately and the Steering Committee will decide whether the patients still on treatment should stop it. Otherwise the trial will continue as planned until the final evaluation. The recruitment into the trial will continue during the preparation of the analysis of the first stage.

18. Criteria for termination of the trial

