5.4. Secondary endpoints

- 5.4.1. Progression-free survival by RECIST 1.1
- 5.4.2. Objective response determined by RECIST 1.1
- 5.4.3. Overall survival
- 5.4.4. Adverse events graded according to CTCAE V4.0

For definitions, see section 14.

6. Trial design, duration and termination

This is a phase II, two-stage single-arm trial evaluating the efficacy of afatinib treatment in pretreated patients with advanced NSCLC harbouring *HER2* exon 20 mutations.

Participating sites will screen patients for *HER2* exon 20 mutations in their local laboratory. One FFPE tumor block must be sent to the central laboratory for later confirmation of the mutations.

Trial patients will receive afatinib 40 mg p.o./day until documented progression or unacceptable toxicity.

Patient accrual is expected to be completed within 24 months including a run-in-period of 6 months. Recruitment will not be stopped after enrolment of the first 9 patients into stage 1 of the 2-stage design. Follow-up will continue until 6 months from enrolment of the last patient. The final report will be prepared 40 months after the inclusion of the first patient. Trial duration is therefore expected to be 40 months.

Approximately six sites from five European countries will participate.

7. Patient selection

Written Informed Consent (IC) must be signed and dated by the patient and the investigator prior to any trial-related intervention or test for eligibility.

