20.3. Independent Data Monitoring Committee

The trial will be presented for review to the ETOP IDMC at each of their semi-annual meetings. Accrual and safety will be monitored. The Stage 1 Report will be reviewed by the IDMC which will make a recommendation to continue or stop the trial based on the results.

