### 1.2 History of the Study

ETOP/7-14 NICHE trial was activated in December 2014 and the first patient was enrolled on September 2015.

The ETOP IDMC reviewed the trial safety data during its scheduled bi-annually meetings, in April 2016 (n=5 patients enrolled; no safety issues identified) and October 2016 (n=13) when the interim analysis was presented. Follow-up was suspended based on the interim analysis and an unscheduled follow-up IDMC meeting in November 2016 on the 13 enrolled patients enrolled).

At the IDMC meeting of October 2016, the interim analysis (1st stage of Simon's two-stage design) was presented. Among the first 9 patients, 5 patients (55.6%) had not reached week 12 free of progression. Thus, the stopping threshold of the 1st stage of Simon's two-stage design was reached, since more than the maximum allowed of 3 patients had a progression by 12 weeks. Based on these results, the IDMC recommended suspending further recruitment into the trial while continuing the treatment and close follow-up for the enrolled patients.

A follow-up analysis, once all enrolled patients reached the 12-week assessment, was performed in November 2016. Among all 13 enrolled patients, 6 patients (46.2%) had not reached week-12 free of progression.

Based on the data and results of the interim analysis and considering the protocol specified early stopping rule, the IDMC recommended that:

- The ETOP 7-14 NICHE trial should be permanently closed to accrual.
- Treatment and follow-up of enrolled patients may continue based on the judgement of the treating physician.
- Patients should be informed.

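### The stage-1 look waits for nine 12-week outcomes with accrual open, although a 4th failure already settles it; acting then would spare a mean of about 2 to 3 enrolments in trials that stop

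*Protocol*

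**What the plan says.** Protocol 17.2 adopts a Simon two-stage design with null DCR 50%, target DCR 75%, one-sided type I error 10% and power 80%: "22 patients need to enter the trial, with 9 patients in the first stage". The trial continues with 6 of 9, and success is at least 14 of 22.

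Section 17.4 fixes when stage 1 is judged: "An early look will take place at the end of the first stage, when 9 patients are evaluable for the primary endpoint". Fewer than 6 with disease control leads to immediate reporting. Two places keep accrual open. Section 6 says "Recruitment will not be stopped after enrolment of the first 9 patients into stage 1 of the 2-stage design", and 17.4 says "The recruitment into the trial will continue during the preparation of the analysis of the first stage".

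On oversight, section 20.3 says "The trial will be presented for review to the ETOP IDMC at each of their semi-annual meetings". Those meetings monitor accrual and safety, and the committee also reviews the Stage 1 Report and recommends whether to continue.

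SAP 1.2 counts the same boundary as failures. It reports that the stopping threshold was reached "since more than the maximum allowed of 3 patients had a progression by 12 weeks". It also records 13 patients enrolled when the interim was presented, with 5 of the first 9 not progression-free at week 12.

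**The concern.** The first stage of a two-stage design exists to limit how many patients enter a trial of a treatment that is not working well enough. Here the outcome takes 12 weeks and planned accrual is about one patient a month, so patients keep entering while the ninth patient's outcome matures.

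Some of that waiting adds nothing to the decision. Once 4 of the first 9 have failed, the other outcomes cannot bring the count to 6. Failures can appear at the week-6 CT (section 15.5), and tumour-assessment forms are due within 14 days of each scan (Table 12), so a running count would be available. What is at stake is avoidable enrolment, not the validity of the test.

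**Working it through.** **Inputs from the documents.** n1 = 9, continue if at least 6; n = 22, success if at least 14; null 50%, target 75% (17.2). Scans at weeks 6 and 12 (15.5). Accrual: 24 months for 22 patients, or 22/24 = 0.92 a month (17.3). Section 6 includes a 6-month run-in within the 24 months; if nobody enters during it, the rate is 22/18 = 1.22 a month.

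**Assumptions, not in the documents.** Random (Poisson) entry, 0 to 70% of failures seen at week 6 and the rest at week 12, and one month from trigger to closure under either rule.

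**1. The plan's own figures.** With X1 the stage-1 successes, P(success) = Σ over x = 6 to 9 of P(X1 = x) × P(at least 14 − x of 13).
- At 50%: 0.1641×0.2905 + 0.0703×0.5000 + 0.0176×0.7095 + 0.0020×0.8666 = 0.097.
- At 75%: 0.2336×0.9198 + 0.3003×0.9757 + 0.2253×0.9944 + 0.0751×0.9990 = 0.807.
- P(stop) = P(X1 ≤ 5): at 50%, (1+9+36+84+126+126)/512 = 382/512 = 0.746; at 75%, 0.166.

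The stated 10% and 80% are met.

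**2. Equivalence.** Four failures leave at most 9 − 4 = 5 successes, which is below 6. Conversely, fewer than 6 successes means at least 4 failures. The two rules therefore give the same decision for every outcome of the first 9, and the figures in step 1 are unchanged.

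**3. Where the 4th failure falls.** P(4th failure is patient k) = C(k−1, 3) × q⁴ × p^(k−4), for k = 4 to 9, where p is the DCR and q = 1 − p. Given a stop, the mean k is 6.68 at DCR 50% and 7.54 at DCR 75%. At 50% it falls at patient 8 or earlier in 85% of stopped trials (1 − 0.1094/0.7461).

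**4. Enrolment avoided.** Twelve weeks is 2.76 months. Under 17.4 as written, mean enrolment at closure is 9 + 0.92×(2.76+1) = 12.4, or 9 + 1.22×(2.76+1) = 13.6.

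If every failure is seen only at week 12, the trigger moves from patient 9 to patient k. The mean saving is then 9 − 6.68 = 2.3 at DCR 50% and 9 − 7.54 = 1.5 at DCR 75%, at either accrual rate. Week-6 failures add to this. Simulation (200,000 trials per row, stopped trials only, DCR 50%) gives:

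| Accrual per month | Failures seen at week 6 | Enrolled, as written | Enrolled, 4th failure | Mean avoided | Trials avoiding none |
|---|---|---|---|---|---|
| 0.92 | 0% | 12.4 | 10.1 | 2.3 | 33% |
| 0.92 | 30% | 12.4 | 9.8 | 2.7 | 25% |
| 0.92 | 70% | 12.4 | 9.3 | 3.2 | 16% |
| 1.22 | 0% | 13.6 | 11.3 | 2.3 | 33% |
| 1.22 | 30% | 13.6 | 10.8 | 2.8 | 25% |
| 1.22 | 70% | 13.6 | 10.1 | 3.5 | 14% |

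The 10th to 90th percentile range is 0 to 6 or 0 to 7. Closure comes 1.9 months (2.3/1.22) to 3.5 months (3.2/0.92) sooner. At DCR 75% the mean saving is 1.5 to 2.5. Averaged over all trials, it is 0.746 × (2.3 to 3.5) = 1.7 to 2.6 at DCR 50%, and 0.166 × (1.5 to 2.5) = 0.2 to 0.4 at DCR 75%.

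**The case against.** A look at n1 is how a Simon design normally works, and open accrual is a deliberate choice stated twice. That stands: this is an optional refinement, and nothing in the test is wrong.

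A reader might infer that the late look defeats the purpose of the two stages. It does not. Closing at 12.4 to 13.6 patients still avoids 8.4 to 9.6 of the 13 second-stage entries (65 to 74%).

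A reader might also infer from SAP 1.2 that the trial actually enrolled about three or four patients needlessly. The SAP does not show that. The history of 13 enrolled and 5 of 9 failed is consistent with the calculation, but no failure dates are given. The November 2016 analysis was done once all 13 had reached their 12-week assessment, so all had entered by about early September. They may all have entered before a 4th failure was known. The patients spared are those entering after that failure, and may include some of the first 9.

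Nor does crossing the boundary oblige the trial to stop: the IDMC recommends (20.3). Section 18.1 also gives general discretion to discontinue, and an unscheduled IDMC meeting was in fact held. These are discretionary and set no trigger at the 4th failure.

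Two practical objections stand and shape the fix. A week-6 response followed by progression at week 12 is unclear, because the summary speaks of control at 12 weeks while 14.1 can attach the 12-week duration to stabilisation only. Scans that are not evaluable also need a rule. Finally, the planned 90% exact interval already ignores the two-stage stop, so that problem is not new, but a smaller stopped trial gives a less precise estimate.

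**Conclusion.** The point holds as a cheap improvement in patient exposure. It is not an error in type I error, power or sample size. The stage-1 boundary is certainly crossed at the 4th failure among the first 9, and nothing in the plan acts on that.

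Among trials that stop at DCR 50% (75% of them), acting then avoids a mean of about 2.3 to 3.5 enrolments. The 10th to 90th percentile range is about 0 to 7, and between one in seven and one in three of these trials avoid none. At DCR 75%, where 17% of trials stop, the mean is about 1.5 to 2.5. The equivalence of the decisions is exact. The size rests on the accrual reading and on the assumed week-6 share and one-month closure time. Because accrual in this trial is permanently closed (SAP 1.2), the point applies to the design as written and to any reuse of it.

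**What to change.** Amend 17.4 along these lines: the stage-1 look takes place when the first 9 enrolled patients have completed the 12-week evaluation, or as soon as a 4th of them has definitively failed the primary endpoint, whichever is first. At the 4th failure new enrolment is suspended, and the Stage 1 Report goes to the IDMC without waiting for its semi-annual meeting.

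Three details belong with it:
- A definitive failure is progression or death that rules out disease control under the endpoint definition used at the look. A not-evaluable scan is not counted before week 12.
- The count runs on the first 9 enrolled, matching the interim cohort in SAP 2.2.
- Patients already enrolled are still assessed at week 12 and included in the DCR estimate.

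Accrual otherwise stays open as in section 6, and 17.4 continues to govern decisions about patients on treatment.

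The cost is a short amendment and a running count from forms already collected. If the trial stops, DCR rests on fewer patients. With interval width roughly proportional to 1/√n, going from 13.6 to 11.3 widens it by √(13.6/11.3) = 1.10, and from 13.6 to 10.1 by √(13.6/10.1) = 1.16, so about 10 to 16%.

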18.1. General criteria for termination of the trial

The trial may be discontinued early in parts or completely if the information on the product leads to doubt as to the benefit/risk ratio, by decision of ETOP or Trial Steering Committee, or at the suggestion of the IDMC based on the interim safety evaluations.

The trial can be terminated at any time if the authorization and approval to conduct the trial is withdrawn by Ethics Committee or regulatory authority decision, insufficient accrual, emerging new data impacting the scientific value of the trial or ethical grounds.

18.2. Discontinuation of protocol treatment for individual patients

Protocol treatment should be stopped in the following situations:

- Disease progression.
- Occurrence of unacceptable toxicities. Stopping protocol treatment is determined by medical judgment of the treating physician.
- Inter-current severe illnesses which would in the judgment of the investigator affect assessments of the clinical status to a significant degree and require discontinuation of protocol therapy. Note: Diagnosis of another neoplastic disease (second malignant tumour) does not mandate a stop of trial therapy; patients may continue to receive protocol treatment after appearance of a second primary tumour, stopping protocol treatment is determined by the medical judgment of the treating physician.
- Request by the patient. Patients have the right to refuse further trial treatment at any time during the trial. Such patients will remain in the trial and will be transferred to the follow-up phase.
- If a patient refuses to have the treatments or follow-up examinations and tests needed to determine whether the treatment is safe and effective.

The decision for discontinuation of protocol treatment of individual patients is taken by the treating physician based on his medical evaluation and taking into account the patient's individual situation.

18.3. Withdrawal of consent

Patients have the right to withdraw consent for further trial participation at any time without having to specify the reason. The data recorded up to the timepoint of withdrawal will continue to be evaluated in the trial. The investigator should ask the patient for consent to continue to collect information on her/his disease and survival status.

It should be documented in both the medical records and in the eCRF, according to the instructions in the ***CRF completion guidelines***, if the patient accepts to be contacted for survival status despite withdrawing the trial consent. For the patient's safety, an end of treatment visit should be performed and documented in the eCRF.

19. Ethics aspects, regulatory approval, and Patient Informed Consent

The Investigator will ensure that this trial is conducted in full conformance with the principles of the “Declaration of Helsinki” or with the laws and regulations of the country in which the research is conducted, whichever affords the greater protection to the individual. The trial must fully adhere to the principles outlined in “Guideline for Good Clinical Practice” ICH Tripartite Guideline (January 1997) or with local law if it affords greater protection to the patient. For studies conducted in the EU/EEA countries, the Investigator will ensure compliance with the EU Clinical Trial Directive (2001/20/EC).

